7.1.8 Handling of Missing Data

In general, with the exception of the primary and secondary variables, missing values are not considered for percentage calculations, unless stated otherwise. In these cases, footnotes will specify the percentage denominator definition.

8. Sample-size Re-assessment and Futility Analysis

8.1. Sample-size Re-assessment

Sample size re-estimation may occur when MMN data from all 3 periods are available for 12 patients, or when 20 patients have been dosed and are expected to complete the study, whichever is sooner. To ensure adequate study power, sample size may be increased up to a total of 40 patients.

The original study SAP describes procedures for a blinded interim analysis and sample size re-assessment. Upon review of the outputs from the blinded interim analysis (which included data only from the first 12 subjects, who had already completed the study), the Sponsor determined that an unblinded analysis of those interim data is necessary to properly inform decisions about study continuation and dose selection. Unblinding of the interim analysis data was thus introduced in Protocol Amendment 4, and the SAP has been modified accordingly.

The unblinded sample size re-estimation procedure will be performed utilizing the following steps:

- 1) Based on treatment allocations, only subjects with evaluable MMN data from all three study periods will be included in the sample size re-estimation.
- 2) Sample size re-estimation calculation will be based on the specifications of approximately 80% power and alpha=0.10 utilizing SAS Proc GLMPOWER for Analysis of Variance and the unblinded group values by treatment assignment (placebo, CVN058 15 mg, CVN058 150 mg) and standard deviation values from the twelve (12) study subjects.

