2.3. Study Rationale

This study will explore central target engagement and proof of mechanism by measuring auditory evoked potential MMN as a pharmacodynamic (PD) marker of CNS response to the selective 5-HT3 receptor antagonist CVN058. It has been reported that subjects with schizophrenia commonly demonstrate a deficit in neural processing that is manifested as a reduction in MMN and impairment of auditory sensory gating (P50) [8]. Other 5-HT3 receptor antagonists have been reported to improve impairments in auditory evoked potentials in schizophrenic subjects. In a study with ondansetron, a widely-prescribed 5-HT3 receptor antagonist, using P50 auditory gating as the auditory evoked potential measure, subjects were given a single dose of ondansetron (16 mg) or placebo in a double-blind, placebo-controlled, randomized and balanced crossover design [9]. Serial measurements of the P50 evoked potential were done at Baseline and 1, 2, and 3 hours after receipt of placebo or ondansetron. The results of the study indicated that ondansetron significantly enhanced P50 auditory gating in subjects with schizophrenia. Tropisetron, a 5-HT3 antagonist that also has α 7 nicotinic cholinergic agonist activity, has similarly been shown to improve P50 auditory gating in subjects with schizophrenia [10].

While the P50 signal is likely a reflection of brainstem and thalamic network activity and is sensitive to antipsychotic treatment, MMN is thought to reflect excitation-inhibition balance in cortical circuits and is not sensitive to antipsychotic treatment [8]. Therefore, to evaluate the potential for CVN058 to improve cognitive function in schizophrenics, MMN will be used as a PD marker. The study will be performed as a 3-way crossover to assess the effect on MMN of CVN058 at two dose levels relative to placebo, with each subject serving as his or her own control to reduce variability. P50 auditory gating will also be measured, as an exploratory endpoint, along with other potentially informative electrophysiological and psychometric parameters.

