4.3. Study Design Summary

In the initial study design, subjects were randomized to 1 of 6 treatment sequences to receive 1 of 3 dose regimens in each period. Each dose regimen consisted of a single oral administration of CVN058 (15 mg or 150 mg initially) or a matching placebo; study drug to be administered with water in the morning. The sequence will determine the order in which a subject will receive each of the 3 regimens. Discontinued subjects may be replaced so that 20 completed subjects are available for analysis.

After the Interim Analysis, the 15 mg dose in each treatment sequence was replaced with a 75 mg dose under Protocol Amendment 4, applicable to all subjects randomized.

Each treatment period is less than 1 day in duration, with a minimum of 7-day washout, maximum 10-day washout between doses. A follow-up telephone call will occur approximately 7-10 days following the last dose received. Subjects may be inpatients or outpatients at the discretion of the Investigator.

At each testing session, subjects will undergo post dose EEG testing including: MMN, P50, qEEG, gamma power, and P300. Testing sessions will begin approximately 1.5 hours post-dose. Prior to dose and at various time points post-dose, blood samples will be collected for the assessment of plasma concentrations of CVN058 and biomarkers.

Study procedures will be conducted at approximately the same times across Treatment Periods to minimize diurnal effects on outcomes. The effect of CVN058 on MMN as well as on exploratory measures (e.g., P50 auditory gating, gamma power, and P300) will be compared to placebo.

5. Determination of Sample Size

Enrollment of at least 20 subjects with schizophrenia (including schizoaffective disorder) is estimated to provide >80% power to detect a median effect size of Cohen's $d=0.5$. Discontinued or withdrawn subjects and subjects for whom MMN is not available for all three study periods may be replaced. The sample size chosen of at least 20 completed subjects is considered to be sufficient to explore the changes in MMN between CVN058 and placebo as well as safety and tolerability of CVN058 in this population. There will be approximately three (3) study sites in the United States. The sample size is subject to re-estimation based on preliminary data.

The sample size re-estimation will occur after twelve (12) subjects have completed all study visits. Full details are discussed in [Section 8](#).

6. Analysis Populations

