7.1.4.1 Primary Analysis

The Primary Endpoint analysis will be performed on the PD population and will consist of a comparison of the post dose PD parameter Mean Amplitude of Duration MMN versus the parameter at time-matched placebo period timepoints using Generalized Linear Models with factors for sequence, subject nested within sequence, period, site and treatment. Two-sided 80% confidence intervals will be constructed for the least squares mean differences between CVN058 and placebo in PD parameters at the post-dose time point for each treatment period.

To maintain overall control of alpha (Type I error rate), the Primary Analysis will employ sequential testing, beginning with the higher dose (e.g., CVN058 150 mg) vs. Placebo using alpha = 0.10 and one-sided significance testing. If significant results are obtained from that first comparison, sequential significance testing of the next lower dose or doses (e.g., CVN058 75 mg) vs. Placebo will then be performed. If the first comparison yields a non-significant result, testing of the latter vs. Placebo will be performed to generate a nominal p-value, but that result will not be formally statistically significant regardless of the p-value.

Effect size will be calculated and summarized for comparisons of CVN058 to Placebo using Cohen's d which expresses the difference between the means of two groups as a function of their pooled standard deviation.

Exposure-response relationships for CVN058 will be explored graphically.

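### The sample-size re-estimation in SAP 8.1 sizes a three-treatment ANOVA that includes the replaced 15 mg dose, not the one-sided within-subject 150 mg contrast of the primary analysis, so its N can be wrong in either direction

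*SAP*

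**What the plan says.** **Re-estimation (SAP 8.1).** Step 1 says that "only subjects with evaluable MMN data from all three study periods will be included in the sample size re-estimation". Step 2 specifies about 80% power and "alpha=0.10 utilizing SAS Proc GLMPOWER for Analysis of Variance and the unblinded group values by treatment assignment". The inputs are listed as "placebo, CVN058 15 mg, CVN058 150 mg) and standard deviation values from the twelve (12) study subjects". N may rise to at most 40.

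**Primary test (SAP 7.1.4.1).** The higher dose is tested first, "vs. Placebo using alpha = 0.10 and one-sided significance testing". The lower dose is tested formally only if the first comparison succeeds. The model has subject nested within sequence, so treatment contrasts are within-subject. Section 7.1.6 makes one-sided 0.10 the default. Section 2.3 gives the reason for the crossover: "with each subject serving as his or her own control to reduce variability".

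**Doses (SAP 4.3).** "After the Interim Analysis, the 15 mg dose in each treatment sequence was replaced with a 75 mg dose under Protocol Amendment 4".

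**Planned size (SAP 5).** At least 20 subjects are said to give more than 80% power for a Cohen's d of 0.5.

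**The concern.** A re-estimation rule should size the test on which the trial will be judged. Step 2 differs from that test in three ways.

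- **Hypothesis.** An ANOVA on three treatment means, with no contrast named, is a 2-df test of any difference among the three. The primary test is a single contrast.
- **Direction.** An F test has no direction. Even a 1-df ANOVA contrast at 0.10 corresponds to one-sided 0.05, not one-sided 0.10.
- **Inputs.** Group values and SDs carry no within-subject correlation unless it is supplied separately. One of the three means belongs to 15 mg, which is no longer given.

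At stake is the decision on how many patients to enrol, from the planned 20 up to 40. If N is too large, patients are exposed without need. If it is too small, the 150 mg comparison is underpowered, and because testing is sequential the lower dose cannot then be formally significant.

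**Working it through.** **Inputs from the SAP:** d = 0.5, N = 20, power above 80% (section 5); alpha 0.10 and 80% power (8.1); one-sided 0.10 within subject (7.1.4.1); cap 40 (8.1).

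**Assumptions, because the SAP gives no interim means, SDs or correlation:** 150 mg effect 0.5 group SD; 15 mg effect from 0 to 1.0 SD; within-subject correlation ρ = 0.5, varied below. The SD of a within-subject difference is SD × √(2(1 − ρ)). At ρ = 0.5 it equals the group SD, so d means the same on both scales.

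**1. Reproduce the planned figure.** For a paired t test, the noncentrality is d√N = 0.5 × √20 = 2.236 with 19 df.
- One-sided 0.10: power 81.7%, which agrees with the stated figure.
- Two-sided 0.10: power 69.5%, which does not.

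So section 5 is consistent with a within-subject, one-sided 0.10 comparison.

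**2. N for the primary test.** The smallest N with 80% power, one-sided 0.10, is 19 (paired t 80.2%). The crossover model with residual df 2N − 4 also gives 19.

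**3. Same contrast, non-directional at 0.10.** N = 27 by paired t (81.2%) or 26 by the crossover model. In the normal approximation the ratio is ((1.645 + 0.842)/(1.282 + 0.842))² = 1.37.

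**4. Three-treatment F test with within-subject error.** The noncentrality is λ = N × Σ(μᵢ − μ̄)²/(1 − ρ), in SD units, with 2 and 2N − 4 df and alpha 0.10. For means (0, 0.25, 0.5) the sum of squares is 0.125, so at N = 33, λ = 33 × 0.125/0.5 = 8.25 and power is 81%.

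**5. Same F test on group SDs, ignoring the correlation.** With N values per treatment, λ = N × Σ(μᵢ − μ̄)² with 2 and 3N − 3 df. Each crossover subject supplies one value per treatment, so N is the number of subjects.

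| 15 mg effect (SD) | Primary test | F, within-subject error | F, group SDs |
|---|---|---|---|
| 0 | 19 | 25 | 48 |
| 0.25 | 19 | 33 | 63 |
| 0.5 | 19 | 25 | 48 |
| 0.75 | 19 | 15 | 28 |
| 1.0 | 19 | 10 | 17 |

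A 15 mg effect of −0.25 gives the same result as 0.75 (15 and 28). The 150 mg effect is fixed at 0.5 throughout; only the 15 mg mean moves the last two columns.

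**6. How noisy that mean is.** With 12 subjects, the standard error of a standardised within-subject difference is about 1/√12 = 0.29. An 80% interval is therefore about ±0.37, wide enough to move N between rows of the table by chance.

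**7. Sensitivity to the correlation.** Here d = 0.5 is held on the group SD. Entries for the primary test are crossover model/paired t where the two differ.

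| ρ | Primary test | F, 15 mg effect 0 | F, 15 mg effect 0.25 |
|---|---|---|---|
| 0 | 37 | 48 | 63 |
| 0.3 | 26/27 | 34 | 45 |
| 0.5 | 19 | 25 | 33 |
| 0.7 | 12 | 16 | 20 |
| 0.8 | 8/9 | 11 | 14 |

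The level changes with ρ, but the mismatch remains at every value.

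**The case against.** **The text is open, not wrong.** GLMPOWER can take a contrast. Section 8.1 does not say outright that the SDs are between-subject, restricting to subjects with all three periods is compatible with within-subject error, and 7.1.6 makes one-sided 0.10 the default. This stands in part: the procedure is not at fault, and the group-SD column is one reading only. But with within-subject error the F test still gives 25 to 33 against 19 for 15 mg effects of 0 to 0.5 SD. Only a set-up that the SAP does not state matches the primary test: a 1-df 150 mg contrast on the residual SD with ALPHA=0.20.

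**15 mg was a real arm at the interim.** This stands. The first 12 subjects received it, no 75 mg data could exist, and summarising it is no error. The fault is letting its mean set N.

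**Other safeguards.** The re-estimation is permissive (it may occur, and N may be increased). Section 8.2 structures the futility analysis like the primary analysis and looks at conditional power up to N = 40. That step is tied to a possible stop, however, so it does not govern the N chosen if the trial continues.

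**Stronger readings that a reader might infer.**
- *That the rule always overstates N.* It does not: the first table shows 15 and 10 against 19.
- *That it calls for 144 to 189 subjects.* That multiplies 48 to 63 per treatment by three, as for parallel groups. In this crossover the figure is 48 to 63 subjects.
- *That it almost always hits the cap.* Even on group SDs, 40 crossover subjects reach 80% power once the largest difference is about 0.55 SD (15 mg equal to placebo or to 150 mg) to 0.63 SD (15 mg midway), not far above the planned 0.5.

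**Conclusion.** The point holds: step 2 of section 8.1 does not size the test in 7.1.4.1, and this is more than missing detail, because the calculation as written gives a different N. At d = 0.5 for 150 mg, 80% power and ρ = 0.5, the primary test needs 19 completers, against 26 to 27 for a non-directional 0.10 contrast and 10 to 33 for the three-treatment F test, depending on the 15 mg mean. Without the within-subject correlation, the F test needs 48 to 63 for 15 mg effects of 0 to 0.5 SD, above the cap.

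The direction is not fixed. With within-subject error, N is too large when the 15 mg effect lies between placebo and 150 mg, and can be too small when it lies well outside that range. An N of 15 would leave the primary test at about 72% to 73% power, and an N of 10 at about 59% to 60% (formulas of steps 1 and 2).

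The sizes rest on assumed means and correlation, since the SAP states no interim values and no re-estimated N. The mismatch itself rests only on the text. The final analysis in 7.1.4.1 is not affected.

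**What to change.** Rewrite step 2 of section 8.1 along these lines:

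- N is the smallest number of completers giving 80% power for the 150 mg versus placebo contrast of 7.1.4.1 at one-sided alpha 0.10, using the within-subject residual SD from the crossover model. Use either a GLMPOWER contrast with ALPHA=0.20 or a one-sided paired calculation.
- The 15 mg data inform the residual SD only, not the effect.
- Power for 75 mg versus placebo is reported separately, from the number of post-amendment completers and a stated assumed effect, because the interim holds no 75 mg data.

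If the calculation has already been run, rerun it this way and document the change and both results. The cost is a paragraph of SAP text and a few lines of code. It needs no new data. Whether enrolment rises or falls depends on the interim values.

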8.2. Interim Futility Analysis

As noted above, the original SAP describes procedures for a blinded interim analysis, while unblinding of the interim analysis was introduced in Protocol Amendment 4. This version (3.0) of the SAP has been modified accordingly to incorporate changes that correspond to the updates in Protocol Amendment 4.

An unblinded interim analysis for futility will be performed when twelve (12) subjects have completed all study visits. An analysis structured identically to the Primary Analysis, unblinded to treatment, will be performed using data only from the first 12 subjects, who have already completed the study. This analysis will utilize the O'Brien-Fleming group-sequential stopping boundary to control alpha (α). SAS Proc SEQTEST will be employed to perform the conditional power analysis for one interim analysis. Study stoppage for futility may occur if conditional power for both active treatment arms is very low.

However, multiple stopping rules may be implemented if preliminary results indicate that the study may yield beneficial results based on other outcome variables. Additional outcome variables to assess in determining study stoppage include, but are not limited to:

- Early phase (120 msec - 200 msec) MMN
- Late phase (200 msec - 260 msec) MMN
- Cohen's d for MMN
- Differences in the secondary endpoints when comparing treatment assignments, utilizing appropriate testing (test selection dependent upon frequency counts) for comparisons of proportions.

Additionally, prior to study stoppage, an assessment will be performed to calculate the conditional power values associated with protocol-permissible increases in the sample size (i.e., up to N=40), based on the observed unblinded data at the time of the interim analysis.

9. Background Characteristics

9.1. Subject Disposition

Study completion and reasons for discontinuation for all randomized subjects in the study will be summarized for each treatment group. Discontinuations by reason will be tabulated for each treatment group. All randomized subjects and study completion status will be presented in a listing.

9.2. Protocol Deviations

All major protocol deviations will be listed.

9.3. Demographic and Baseline Characteristics

Continuous demographic variables (e.g., age, height, weight) will be summarized by descriptive statistics for each treatment group. Qualitative demographic characteristics (e.g., gender, race, ethnicity) will be summarized by counts and percentages for each treatment group. Demographics will also be presented in a subject listing.

9.4. Prior and Concomitant Medications

Per protocol, medications that might inhibit or mask the effects of CVN058 are not permitted as concomitant medications. These include serotonin reuptake inhibitors which increase synaptic serotonin levels, as well as drugs that bind to 5-HT3 receptors at clinically relevant concentrations or are reported to inhibit signaling through 5-HT3 non-competitively, including some antipsychotic drugs [14], [15], [16]. Permissible antipsychotic medications are risperidone (Risperdal), haloperidol (Haldol), quetiapine (Seroquel), aripiprazole (Abilify) and paliperidone (Invega).

All medications taken during the course of the study with a start date or an end date on or after the date of the first study treatment or marked as ongoing will be considered concomitant. Medications stopped prior to the date of the first study treatment will be considered prior medications.

If start and/or end dates for medications are missing, the dates will be imputed as described below.

Imputing partial or missing start dates:

- If the year is unknown, the start date will not be imputed. The data will remain missing.
- If the month is unknown, and the year is the same as the first treatment date of the study, and the corresponding stop date is not prior to the first treatment date of the study, then impute the month and day of the date to be equal to the first dose month and day. Otherwise, impute the month as January.
- If the day is unknown and the month and year are the same as the first treatment date of the study, and the corresponding stop date is not prior to the first treatment date of the study, then impute the day to be equal to the day of the first treatment. Otherwise, impute the day as '01'.

Imputing partial or missing end dates:

- If the year is unknown, the end date will not be imputed. The data will remain missing.
- If the month is unknown, impute the month as December.
- If the day is unknown, impute the day to be the last day of the month.

If an imputed stop date is greater than the last medication date or study completion/discontinuation date, then the imputed stop date will be set equal to the maximum of these two dates (last medication date or completion/discontinuation date).

The number and percentage of subjects using each concomitant medication will be summarized for each dose group according to the World Health Organization Drug Dictionary (WHODRUG) (Version 01 March 2018) Anatomic Therapeutic Class (ATC) Level II preferred term. Subjects with multiple use of a concomitant medication during a treatment period will be counted only once for a given drug class or Preferred Term (PT) for the treatment period. Medication summaries will be based on the Safety Population (SAF) and presented in summary tables and a subject listing.

9.5. Medical History

Medical history (prior and ongoing medical illness) will be coded using the Medical Dictionary for Regulatory Activities (MedDRA, Version 21.0) coding dictionary. Medical history to be obtained will include determining whether the subject has any significant conditions or diseases relevant to the disease under study that stopped at or prior to signing of informed consent. Ongoing

conditions are considered concurrent medical conditions. Medication history information to be obtained includes any medication relevant to eligibility criteria stopped at or within 45 days prior to signing of informed consent.

Prior and ongoing medical conditions will be summarized by presenting for each group the number and percentage of subjects having any condition. Prior and ongoing conditions will be presented in separate Medical History tables.

Subject data listing of all medical history will also be presented.

10. Adjustments for Covariates

Randomization for this study will be stratified by the study site in which subjects are enrolled. The model for the primary analysis will include this stratification variable as a main effect. This stratification variable may also be included as a factor for select secondary variables. Baseline values will also be used as a covariate when baseline is available for the endpoint.

11. Safety Analysis

All safety analysis will be based on the SAF population. Analysis using the SAF population will be based on the actual treatment received.

11.1. Pre-treatment Events and Adverse Events

All Pre-treatment Events (PTEs) will be presented in a subject-level listing.

Adverse events and medical conditions will be coded using the Medical Dictionary for Regulatory Activities (MedDRA) (Version 21.0). Treatment-emergent adverse events (TEAEs) will be defined as any event with onset during or after the first dose of study treatment (active or placebo).

Treatment-emergent adverse events will be summarized for each treatment group by presenting the number and percentage of subjects having any treatment-emergent AE, having an AE in each body system, and having each individual AE. (Note: In any given category [e.g., body system] a subject will only be counted once.)

Serious TEAEs, TEAEs by severity and TEAEs by relationship to study drug will also be summarized by treatment group.

All AEs will be presented in a subject-level listing.

